## Evaluating the Impact of an Emotion Regulation Intervention on Emotion Perception

### Purpose of the Study

**Aim 1:** To evaluate the short-term impacts of an emotion regulation intervention on emotion perception in the laboratory. In the laboratory training session, we will compare performance on behavioral emotion perception tasks between participants who receive the intervention, a training in an emotion regulation skill (i.e. mindful breathing), and participants in the control conditions (perspective-taking and worry inductions). **Hypothesis 1:** We predict that participants in the emotion regulation intervention condition will show less negative bias in their performance compared to participants in the control conditions. We also predict that intensity of emotional distress will be associated with negative biases.

**Aim 2:** To investigate the longitudinal effects of this intervention on emotion perception outside the lab using experience sampling. After the laboratory training session in aim 1, participants in both groups will receive an auditory reminder of the emotion regulation skill (a specific tone) three times a day through their mobile phones for one week and then will complete emotion perception tasks. Using our method of generalization, the participants in the intervention group have learned to associate the tones with reductions in emotional distress. For this aim, we will compare changes in performance on the emotion perception tasks over time between the three groups. **Hypothesis 2:** We predict that these cues will lead to greater decreases in negative biases in emotion perception over time compared to the control conditions. We will also test whether changes in emotional distress and regulation mediate the longitudinal changes in emotion perception performance.

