Condition 1: Mindful Breathing. Participants assigned to this condition will first receive an orientation to mindful breathing, an emotion regulation skill based on Mindfulness Based Stress Reduction (Kabat-Zinn, 1990). The experimenter will orient them to the concept of focusing attention on the breath while feeling intense emotions, explaining that it's an active skill that one can use to calm down when distressed. After the initial orientation, participants are instructed to participate in the stressor task while practicing the mindful breathing skill. Reductions in emotional arousal will be continuously monitored using a real-time monitoring program that samples arousal through skin conductance every 500ms relative to the average baseline arousal. Emotional distress will also be assessed repeatedly throughout the task (SUDS). Once participants reduced their sympathetic arousal (returning to baseline in skin conductance) in the stressor task, a novel tone will be heard through the headphones. Through classical conditioning, participants learn to associate this specific sound with reductions in negative emotional arousal and distress.

Condition 2: Habituation. This comparison condition will most closely resemble the procedures of the previous study on generalizing emotion regulation (Pro00035922). Participants will hear each stressor for a minimum of 2 and a maximum of 4 times. Reductions in emotional arousal will be continuously monitored using a real-time monitoring program that samples arousal through skin conductance every 500ms relative to the average baseline arousal. Emotional distress will also be assessed repeatedly throughout the task (SUDS). Once participants reduced their sympathetic arousal (returning to baseline in skin conductance) in the stressor task, a novel tone will be heard through the headphones. Through classical conditioning, participants learn to associate this specific sound with reductions in negative emotional arousal and distress.

Condition 3: Control. This control condition will only present the stressor task without further instructions. Although emotional distress (SUDS) and sympathetic arousal (SCR) will be measured in this task as the first condition, participants in this condition will not hear the tones.

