Immediately after the emotional stressor task, all participants will again report: 1) subjective units of general psychological distress (SUDS; visual analogue scale from 0-9), 2) dissociation state, assessed using self-report (Dissociative-Tension States Scale 4 item version-DSS-4 from the DSS-acute), 3) levels of arousal with the Sedation Scale, and 4) current affect with the PANAS-2. They will then complete the laboratory emotion perception bias task and a manipulation check. Afterward, they will be oriented to the mobile phone prompts they will receive during the testing phase.

Testing Phase: During the one-week testing phase, participants in both conditions will receive three text-message prompts through their own phones randomly each day. These prompts will function both as an EMA measurement of self-reported negative emotional distress, as well as the delivery method of the tones. We will have a specific application, processed and stored on Heroku, that will receive and send text messages to participants via Twilio. In each prompt, participants will be asked to report on their current negative emotional distress (SUDS). When participants report high distress (i.e.,  $SUDS > 2$ ), they will automatically hear the tone by receiving a text message with an .mp3 file. The participants in the control conditions will also hear the tone despite having no previous associations with it, to control for potential placebo effects. After hearing this sound, participants will report again on

their distress, then complete the phone-based emotion perception task. As a manipulation check, the participants in the emotion regulation intervention condition will be asked if they actually used the mindful breathing skill. If the participant does not meet criterion for high distress, they will instead receive a text response on their phone thanking them for their response (see text message sample script document).

All participants will complete the laboratory emotion perception tasks and self-report measures of emotion and psychological functioning through an online Qualtrics survey at the end of this testing phase. They will also complete an exit questionnaire through this Qualtrics survey (see exit questionnaire document).

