Specific Aim 1: Aim 1 will determine if the emotion regulation intervention leads to fewer negative biases in emotion perception during the laboratory training session. For this aim, we will conduct ANCOVA analyses to study group differences in performance on the emotion perception laboratory tasks, controlling for their baseline scores assessed in the intake session. To compare the conditions' impacts on negative biases, we will analyze group differences in 1) number of trials with neutral facial expressions are misclassified as negative emotions; 2) accuracy for positive emotions and negative emotional expressions. We will also examine the relationship between emotional distress and emotion perception. Hypothesis 1: Participants in our emotion regulation condition will have less negative bias in emotion perception (e.g. fewer neutral faces misclassified as negative, lower accuracy for negative emotions, higher accuracy for positive emotions) compared to participants in both the control conditions. Even though the perspective-taking and mindful breathing conditions may have similar effects (e.g. increasing attention to social cues (Olsson et al., 2016; Quaglia, Goodman, & Brown, 2016)), perspective-taking inductions may still lead to mood-congruent biases by increasing negative emotional responses (Lamm, Batson, & Decety, 2007). Therefore, we predict that the emotion regulation intervention would reduce this bias significantly more than both the worry and perspective-taking conditions. We also predict that intensity of emotional distress will be related to negative biases in emotion perception.

Specific Aim 2: Aim 2 will compare the changes in emotion perception over time between the emotion regulation breathing condition and the control conditions. For this aim, Multilevel modeling (MLM) will be used because it permits evaluation of longitudinal data on participants over time with trajectories for each participant examined as random effects. We will conduct MLM analyses to study group differences in changes in the laboratory emotion perception tasks assessed during intake (time 1), the training session (time 2) and after the testing phase (time 3). For the phone-based behavioral task, we will first examine the psychometric properties of this measure in this clinical sample. Then, we will analyze group

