differences in the valence of emotion perception ratings over the one-week testing phase. We will also examine whether changes in emotion dysregulation and distress mediate changes in negative biases over time. Finally, we will also explore the effects of the intervention on self-reported psychological and social functioning. Hypothesis 2: One week of hearing the tones via mobile phones will lead to greater long-term changes in negative biases emotion perception for participants in the emotion regulation condition compared to the participants in the control conditions. Changes in emotional regulation and distress over time will mediate changes in negative biases in emotion perception over time.

If our hypotheses are not supported and the conditions do not have significantly different effects on emotion perception, these findings would be indicative of trait-like deficits in emotion perception beyond the momentary effects of mood or perspective-taking. We would then use moderation analyses to explore the role of other stable factors within emotion perception performance, such as trait empathy (measured by the IRI) or psychiatric diagnoses.

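### Hypothesis 2 credits the phone tones, but the Aim 2 model compares arms that also differ in training, so a training effect that lasts would be reported as a tone effect

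*Combined protocol and SAP*

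**What the plan says.** Purpose of the Study (Aim 2) puts the cause in the cues: "We predict that these cues will lead to greater decreases in negative biases in emotion perception over time compared to the control conditions". Data Analysis & Statistical Considerations repeats this as Hypothesis 2: "One week of hearing the tones via mobile phones will lead to greater long-term changes in negative biases emotion perception".

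The analysis is by randomised arm: "Aim 2 will compare the changes in emotion perception over time between the emotion regulation breathing condition and the control conditions". The model is an MLM of group differences in change on the laboratory tasks, "assessed during intake (time 1), the training session (time 2) and after the testing phase (time 3"). No contrast among the three times is named.

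Under Experimental Procedures, Condition 1 is taught mindful breathing and has a tone paired with the return of arousal to baseline. Condition 2 (Habituation) has the same pairing without the skill. Condition 3 (Control) has the stressor only, and "participants in this condition will not hear the tones" at training. In the Testing Phase the tone goes to participants in every arm who report SUDS above 2, with the stated purpose of controlling for placebo effects. As a manipulation check, "the participants in the emotion regulation intervention condition will be asked if they actually used the mindful breathing skill"; no analysis of the answer is described.

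At the training session, after the stressor task and before any phone prompt: "They will then complete the laboratory emotion perception bias task and a manipulation check".

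**The concern.** The claim and the test have different null hypotheses. The claim's null is that a week of tones does nothing. The model's null is that the arms do not differ in change for any reason. Only the training condition is randomised, and no arm receives breathing training without tone pairing. Sending the tone to all arms deals with the placebo effect of a sound. It does not separate a conditioned tone from training that lasts, or from breathing practised without a prompt.

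The plan itself expects the rival explanation to operate. Hypothesis 1 predicts an arm difference at the training session, before any phone tone. If that difference simply persists, the intake-to-end comparison is positive with inert tones. Aim 2 is the test of the generalisation method, and Background & Significance says the findings will inform larger trials. A misattributed result would mislead them about which component to carry forward.

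**Working it through.** **Inputs.** From Data Analysis & Statistical Considerations: 24 completers per arm (72 in all), two-sided 5%, f = 0.38, power at least 80%. Assumed, because the documents give no figure: correlation ρ between time points of 0.3, 0.5 or 0.7; the share p of the training effect still present at end of week; SD 1 at each time. Effects are expressed as reductions in bias.

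**The plan's own figure.** Three-group F test, noncentrality f²N = 0.38² × 72 = 10.4 on 2 and 69 df: power 81.3%. The stated 80% reproduces and is not in dispute.

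**Effect size for one arm against two equal arms.** With means (d, 0, 0), f = d√2/3, so d = 0.38 × 3/√2 = 0.806.

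**Inert tones, time 3 adjusted for intake.** Mindful Breathing against the pooled comparators has SE = √(1−ρ²) × √(1/24 + 1/48) = 0.25√(1−ρ²), which is 0.238, 0.217 and 0.179 at the three correlations. The expected t is 0.806p/SE. For example, p = 0.5 and ρ = 0.5 give 0.403/0.217 = 1.86 against a critical value of 1.995 (68 df). Share of simulated trials in which Mindful Breathing is significantly better (6,000 per cell; the noncentral t formula agrees within about two points):

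| Persistence p | ρ = 0.3 | ρ = 0.5 | ρ = 0.7 |
|---|---|---|---|
| 0% | 2.3% | 2.0% | 2.2% |
| 25% | 12.7% | 13.6% | 20.3% |
| 50% | 37.8% | 43.1% | 60.2% |
| 100% | 90.0% | 95.8% | 99.3% |

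Requiring Mindful Breathing to beat each comparator separately lowers this to about 16–32% at 50% persistence and 71–95% at 100%.

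**Tests closer to the planned MLM.** With inert tones and the whole d = 0.806 kept, group by linear time over times 1–3 rejects in 66%, 81% and 96% of trials at ρ = 0.3, 0.5 and 0.7. Group by categorical time rejects in 69%, 85% and 98%.

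**The time 2 to time 3 contrast.** In the same fully persistent setting, the three-arm test of change from time 2 to time 3 rejects in about 5%, its nominal level. In the direction of Hypothesis 2, Mindful Breathing against the pooled comparators is significant in at most 2.6% of trials at full persistence and at most 0.5% at 25–75%. Fading pushes the contrast the other way: at 50% persistence it favours the comparators in about 27–54%.

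**Its price.** The SE of the contrast is 0.25√(2(1−ρ)), or 0.296, 0.250 and 0.194, larger than the adjusted time 3 SE at every correlation. An effect added during the phone week of 0.403 SD (half of 0.806) would be detected in about 27%, 36% and 54% of trials.

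**The case against.** The strongest reply is that the plan already collects a measurement after training and before the phone tones, and puts it in the MLM. That stands. A reader might infer that the design cannot separate persistence from the phone week at all; the time 2 bias task shows otherwise. The fault is that the contrast using it is not named, while the hypothesis is worded as if it were.

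A second reply is that breathing prompted by the tone is the intended mechanism, since Aim 2 describes the tone as a reminder of the skill. That also stands, and it narrows the rival explanation to persistence and uncued practice. The skill-use question, as described, does not separate cued from uncued use.

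A third temptation is to treat Habituation against Control as a clean test of the tones, because neither arm is taught a skill. The documents do not support this. Habituation is itself a training procedure, with each stressor heard 2 to 4 times while arousal is monitored. The description of the stressor task says three presentations, and the two passages need reconciling. If a habituation effect of 0.806 SD persisted at 25%, 50% or 100% with inert tones, that contrast would favour Habituation in about 10–16%, 29–49% and 81–97% of trials. Nor is it right that the plan leaves this pair out altogether: Aim 2 compares three groups, so the pair sits inside the overall test, though no pairwise contrast is named.

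**Conclusion.** The concern holds as one of attribution. The intake-to-end arm comparison estimates training, tone pairing and phone week together, and Hypothesis 2 assigns the whole of it to the tones. With inert tones and a training effect of the planned size, the plan would credit the tones in roughly 13–20% of trials at 25% persistence, rising to 90–99% at full persistence. These figures rest on assumed persistence and correlations, normal scores, equal comparators and a pooled comparison.

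A reader might take them as inflated type I error. They are not: the arms do differ in these scenarios, and the model is right to say so. What is wrong is the cause named. If nothing persists, the rate is nominal, and the documents give no figure for how much of a single session's effect lasts a week.

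**What to change.** 1. Reword Hypothesis 2 and its conclusion, in Purpose of the Study and in Specific Aim 2. The arm comparison from intake to end of week should be described as the combined effect of training, tone pairing and the phone week, not as the effect of the tones.
2. Prespecify, from the same MLM, the group difference in change from time 2 to time 3 on the emotion perception bias task as the contrast for any added effect of the phone week. State its limits: it still includes breathing practised without the tone; fading of the training effect works against Hypothesis 2; and Experimental Procedures lists no BLERT at the training session, so it covers the bias task only.
3. Report Habituation against Control as exploratory at most, and not as an isolated tone effect.
4. Reconcile the arm definitions first. Purpose of the Study, Background & Significance, Potential Benefits and Specific Aim 1 name worry and perspective-taking comparators. Study Overview and Experimental Procedures name Habituation and Control. The Testing Phase says the control conditions have no prior association with the tone, which does not fit Habituation as described.

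No new data, visits or participants are needed. The cost is a narrower headline conclusion and one more prespecified contrast, likely with lower power than the intake-to-end comparison.

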## Data Analysis & Statistical Considerations

For the primary outcome of biases in emotion perception, the estimates were derived from a mean difference between conditions. With a Type-I error rate of 5% and 72 participants (24 per group), we will have at least 80% power to detect a medium to large effect size (Cohen's  $f = 0.38$ ), based on previous research demonstrating negative biases in emotion perception using similar behavioral measures. (Schmid & Schmid Mast, 2010) Because we anticipate a 10% to 15% rate of dropout, 30 participants will be randomized to each group. Therefore, this study will recruit 90 adult participants over the age of 18 who have high emotion dysregulation and interpersonal problems.

Since 2004, the CBTRP has recruited a range of adult psychiatric samples all characterized by problems with emotion regulation. Across studies of emotional functioning, it is estimated that our lab has run over 980 participants since 2004, at a rate of roughly 90 per year. In our previous NIMH project, over 33 months we have screened 1154 individuals and enrolled 169 participants, at a rate of 5.12 per month. We project enrolling 90 participants over 14 months, at a rate of 6.43 per month. Given our demonstrated track record of success meeting the required recruitment target in the present application, we expect to meet recruitment targets in the proposed project.

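### A null result is to be read as pointing to trait-like deficits, which non-significance at about 24 per group cannot show

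*Combined protocol and SAP*

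**What the plan says.** All quotes are from Data Analysis & Statistical Considerations.

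- **Trigger and conclusion.** After Hypothesis 2 the plan gives a condition, "If our hypotheses are not supported and the conditions do not have significantly different effects on emotion perception", and its consequence: "these findings would be indicative of trait-like deficits in emotion perception beyond the momentary effects of mood or perspective-taking". Exploratory moderation analyses (trait empathy, diagnosis) would follow.
- **Size.** With 72 participants, 24 per group, and a 5% type I error, "we will have at least 80% power to detect a medium to large effect size", given as Cohen's f = 0.38. On recruitment: "Because we anticipate a 10% to 15% rate of dropout, 30 participants will be randomized to each group".
- **Aim 1 analysis.** ANCOVA of the laboratory tasks, "controlling for their baseline scores assessed in the intake session". The relationship between distress and emotion perception is also to be examined.
- **Aim 2 distress analysis.** "We will also examine whether changes in emotion dysregulation and distress mediate changes in negative biases over time".
- **Expected similarity of arms.** Hypothesis 1 grants that "the perspective-taking and mindful breathing conditions may have similar effects" but still predicts that the intervention will "reduce this bias significantly more than both the worry and perspective-taking conditions".

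No confidence-interval rule, equivalence margin or smallest effect of interest is stated.

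**The concern.** The sentence attributes a null to one explanation, stable deficits, when the design cannot separate that from at least three others:

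1. A real effect of momentary distress that is smaller than the one the trial is sized for.
2. A manipulation that did not make the arms differ in distress, which leaves the mood account untested.
3. For the contrast of the intervention with a given comparator, a comparator that acts in the same way. Under Experimental Procedures, Mindful Breathing and Habituation both pair the tone with a return of arousal to baseline.

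No estimate, test or sample size depends on the sentence. What is at stake is the stated conclusion of a null trial about the mechanism the study is meant to test. Background & Significance says the findings will inform larger trials, so a mistaken trait reading could count against the emotion-regulation approach without evidence against it.

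**Working it through.** **Inputs from the plan:** alpha 0.05; three groups; N = 72 (24 per group); f = 0.38; 90 randomised; 10% to 15% dropout. At 10% dropout, 90 × 0.90 = 81 are analysed (27 per group).

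**Assumed:** baseline-outcome correlation r of 0.5 or 0.7, which the plan does not give; f = 0.25 on the unadjusted scale as an illustrative medium effect.

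**1. The plan's own figure.** Noncentral F with df 2 and N − 3 and λ = N f². At N = 72 and f = 0.38, λ = 72 × 0.1444 = 10.40 and power is 0.813. The claim of at least 80% reproduces.

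**2. What these effects mean in SD.** For means (d, 0, 0), f = d√2/3, so d = 3f/√2. This gives 0.81 SD at f = 0.38 and 0.53 SD at f = 0.25.

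**3. Chance of missing f = 0.25.** For ANCOVA, df are 2 and N − 4, and λ = N f²/(1 − r²).

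| N | Analysis | λ | Power | Missed |
|---|---|---|---|---|
| 72 | ANCOVA, r = 0.5 | 6.00 | 0.564 | 44% |
| 72 | ANCOVA, r = 0.7 | 8.82 | 0.742 | 26% |
| 72 | No adjustment | 4.50 | 0.443 | 56% |
| 81 | ANCOVA, r = 0.5 | 6.75 | 0.620 | 38% |
| 81 | ANCOVA, r = 0.7 | 9.93 | 0.796 | 20% |

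The ANCOVA rows match the planned analysis. The unadjusted row is for reference.

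**4. What a null can exclude.** The pairwise 95% half-width is t × √(2/n) × √(1 − r²). With n = 24, t is about 1.995 and √(2/24) = 0.289. The half-width is 0.58 SD at r = 0, 0.50 at r = 0.5 and 0.41 at r = 0.7. An observed difference of zero would leave true differences of 0.4 to 0.5 SD inside the interval.

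**5. Does similarity of two arms explain a null?** For means (d, d, 0) the overall mean is 2d/3 and the squared deviations sum to 6d²/9. That equals the sum for (d, 0, 0), so f = d√2/3 in both cases and omnibus power is the same (0.813 at d = 0.806). Two similar arms do not make an omnibus null more likely. They do explain a null in the contrast between those two arms.

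**6. Distress-bias association.** Treated as a simple correlation (Fisher z, N = 72), power is 73% at a true correlation of 0.30 and 39% at 0.20.

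**7. Between-arm distress difference.** For a true 0.5 SD difference with 24 per group (noncentral t, pooled df), power is 40% unadjusted, and 51% or 67% with a baseline covariate at r = 0.5 or 0.7.

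**The case against.** The wording is only that findings would be indicative, and the one action that follows is exploratory moderation. That is fair and limits the stakes, but the sentence still picks one explanation before the data are seen.

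The stronger objection is that the trigger needs more than non-significant group differences: the hypotheses must also be unsupported. Hypothesis 1 includes a link between distress and bias. Read as a pooled association, it does not need the arms to separate, so it could appear even if the manipulation failed. It is a partial safeguard, with 73% power at a correlation of 0.30. It is not decisive: power is 39% at 0.20, and the plan states none for it. The mediation analysis likewise implies a path from group to distress.

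Four stronger readings are tempting, and the documents do not support them:

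- *The plan has no between-arm distress information.* Mediation implies some. What is missing is any tie between it and the inference.
- *The sample size is wrong.* It reproduces, and 90 randomised covers the stated dropout.
- *Similar arms explain any null.* They do so only for the contrast concerned (step 5).
- *The miss rates show how often the trait conclusion would be wrongly drawn.* They are for one Aim 1 outcome and are upper bounds on how often the rule applies, because it also requires unsupported hypotheses.

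**Conclusion.** The inference is unsound as written. A null at this size is compatible with a moderate effect of momentary distress: under the planned ANCOVA, f = 0.25 is missed in 44% or 26% of trials at N = 72, and in 38% or 20% with 81 analysed. These figures rest on assumed baseline correlations of 0.5 and 0.7 and on an illustrative effect size. At higher correlations the problem shrinks, but non-significance alone would still not establish a trait.

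A reader might also infer that a null outcome together with a clear distress difference would be evidence against a mood effect. It would not be by itself: the outcome interval still decides what is excluded, and a claim of no effect needs a margin justified beforehand.

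Two separate defects bear on any reading of a null. The arms are Mindful Breathing, Habituation and Control in Study Overview and Experimental Procedures, but the comparators are perspective-taking and worry in Purpose of the Study, Background & Significance, Potential Benefits and the analysis section. SUDS runs 0-100 under Measures and Tasks, and 1-9 and then 0-9 in the training session. Each set must be reconciled in its own right.

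**What to change.** 1. Delete the trait-like inference.
2. State that if the contrasts are not significant the result is inconclusive. Report the baseline-adjusted difference between the intervention and each comparator, and the distress-bias association, with 95% confidence intervals. Conclude only that effects outside those limits are excluded.
3. Name in advance one distress measure already collected (for example post-stressor SUDS or PANAS-2, or skin conductance during the stressor task). For each contrast, report its between-arm difference with a 95% interval, as context for whether the manipulation separated the arms and not as a pass/fail gate.
4. Require a pre-stated, justified margin only if absence of an effect is to be claimed.
5. Keep the moderation analyses exploratory, as now.
6. Reconcile the arm descriptions and, if SUDS is the measure named, its range.

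**Cost.** One paragraph of wording and the choice of one measure; no new data and no change to the primary model. The downside is that a null trial supports a weaker claim, and the distress comparison will often be imprecise too (40% to 67% power at 0.5 SD with 24 per group).
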